5.1.2 Secondary Endpoints

- Change from baseline in dyspnea using the University of California San Diego Shortness of Breath Questionnaire (UCSD SOBQ) at week 12;
- Change from baseline in SGRQ total score at week 24;
- Change from baseline in dyspnea using UCSD SOBQ at week 24;
- Percentage of patients with on-treatment Serious Adverse Events (SAE) from baseline to week 24.

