5.3.7 Adverse event collection and reporting

AE Collection

The investigator shall maintain and keep detailed records of all AEs in the patient files.

The following must be collected and documented on the appropriate eCRF by the Investigator:

- From signing the informed consent onwards through the Residual Effect Period (REP), until individual patient's end of trial: all AEs (serious and non-serious) and all AESIs. However, if an individual patient discontinues trial medication prematurely but stays in the trial (i.e. if further visits incl. telephone visits, or vital status assessments are planned) from then on and until the individual patient's end of the trial the Investigator must report related SAEs and related AESIs.
- After the individual patient's end of trial: the investigator does not need to actively monitor the patient for AEs but should only report relevant SAEs and relevant AESIs of which the investigator may become aware of.

[figure not shown]

Figure 5.3.7:1 AE Collection

The Residual Effect Period (REP) is defined as 28 days after the last trial medication administration. All AEs which occurred through the treatment phase and throughout the REP will be considered as on treatment please see [section 7.3.4](#). Events which occurred after the REP will be considered as post treatment events.

AE reporting to sponsor and timelines

The Investigator must report SAEs, AESIs, and non-serious AEs which are relevant for the reported SAE or AESI, on the BI SAE form via fax immediately (within 24 hours) to the sponsor's unique entry point (country specific contact details will be provided in the ISF).

The same timeline applies if follow-up information becomes available. In specific occasions the Investigator could inform the sponsor upfront via telephone. This does not replace the requirement to complete and fax the BI SAE form.

With receipt of any further information to these events, a follow-up SAE form has to be provided. For follow-up information the same rules and timeline apply as for initial information.

For Japan only: All SAEs must be reported immediately to the head of the trial site. With receipt of any further information to these events, a follow-up SAE form has to be provided. For follow-up information the same rules and timeline apply as for initial information.

Information required

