7.3.2 Secondary endpoint analyses

Change from baseline in UCSD SOBQ at week 12 will be analysed using the same method as the primary endpoint, but with baseline UCSD SOBQ instead of SGRQ total score as covariate. Data collected after visit 5 (planned 12 weeks after start of study treatment) will not be used for this analysis.

Both changes from baseline in SGRQ and UCSD SOBQ at week 24 will be analysed as in the respective week 12 analysis. For these analyses, data collected from the complete 24 weeks treatment period will be used.

Percentages of patients with on-treatment SAEs from baseline to week 24 will be compared using the Cochran-Mantel-Haenszel test adjusting for the categorical covariate presence of any echocardiographic signs indicative of right heart dysfunction (yes/no). Adjusted Mantel-Haenszel type risk ratios and risk differences with 95% confidence intervals will be used to quantify the treatment effect for the comparison between treatment groups.

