7.3.4 Safety analyses

Analysis of key safety endpoints is described in [sections 7.3.2](#) and [7.3.3](#).

Adverse events will be coded using the Medical Dictionary for Regulatory Activities (MedDRA) coding dictionary. Standard BI summary tables and listings will be produced. All adverse events with an onset between start of treatment and end of the residual effect period (REP), a period of 28 days after the last dose of trial medication, will be assigned to the treatment period for evaluation.

All treated patients will be included in the safety analysis. In general, safety analyses will be descriptive in nature and will be based on BI standards. No hypothesis testing is planned.

Statistical analysis and reporting of adverse events will concentrate on treatment-emergent adverse events. To this end, all adverse events occurring between start of treatment and end of the residual effect period will be considered 'treatment-emergent'. The residual effect period is defined as 28 days. Adverse events that start before first drug intake and deteriorate under treatment will also be considered as 'treatment-emergent'.

Frequency, severity, and causal relationship of adverse events will be tabulated by system organ class and preferred term after coding according to the current version of the Medical Dictionary for Drug Regulatory Activities (MedDRA).

Laboratory data will be analysed both quantitatively as well as qualitatively. The latter will be done via comparison of laboratory data to their reference ranges. Values outside the reference range, as well as values defined as clinically relevant, will be highlighted in the listings. Treatment groups will be compared descriptively with regard to distribution parameters as well as with regard to frequency and percentage of patients with abnormal values or clinically relevant abnormal values.

Vital signs, physical examinations, or other safety-relevant data observed at screening, baseline, during the course of the trial and at the end-of-trial evaluation will be assessed with regard to possible changes compared to findings before start of treatment.

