## **6. GENERAL ANALYSIS DEFINITIONS**

### **6.1 TREATMENTS**

The following trial periods will be defined: screening, post-randomisation, treatment period, off-treatment, residual effect period, follow-up and post-study as follows:

Note: the last day of each of the following periods is excluded.

- Screening: from informed consent to randomisation
- Post-randomisation (optional): from randomisation to first randomised trial drug intake in treatment period
- Treatment period: from first randomised trial drug intake (or re-start of treatment if interruption) to last randomised trial drug intake (or the day before start date of interruption, if interruption) plus one day
- Off-treatment (optional): from start date of interruption to re-start of treatment
- Residual effect period (optional): from the last trial drug intake plus one day to last trial drug intake plus 28 days plus one day
- Follow-up (optional): from last trial drug intake plus 29 days up to the beginning of post-study period. This period is only created if last trial drug intake took place more than 28 days before trial completion, or for patients having prematurely discontinued the treatment and still continuing the trial

- Post-study: from the latest of last trial drug intake plus 29 days / date of trial completion / follow-up visit / early end of treatment visit plus 1 day to database lock

For safety analyses, data up to 28 days after last trial drug intake (included) will be considered on-treatment. For on-treatment efficacy analyses, data up to the day after last trial drug intake (included) will be considered.

For safety and efficacy analyses, patients will be assigned to the treatment group they were randomised to.

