### **7.8.1 Adverse events**

Unless otherwise specified, analyses of adverse events will be descriptive in nature and will be based on BI standards (6). No hypothesis testing is planned. All analyses of AEs will be based on the number of patients with AEs and NOT on the number of AEs.

Furthermore, for analysis of AE attributes such as duration, severity, etc. multiple AE occurrence data on the CRF, will be collapsed into AE episodes provided that all of the following applies:

- The same MedDRA lowest level term was reported for the occurrences
- The occurrences were time-overlapping or time-adjacent (time-adjacency of 2 occurrences is given if the second occurrence started on the same day or on the day after the end of the first occurrence)
- Treatment did not change between the onset of the occurrences OR treatment changed between the onset of the occurrences, but no deterioration was observed for the later occurrence

For further details on summarization of AE data, please refer to the guideline “Analysis and Presentation of Adverse Event Data from Clinical Trials” (6).

The analysis of adverse events will be based on the concept of treatment emergent adverse events. That means that all adverse events occurring between first drug intake until 28 days after last drug intake (end of the residual effect period) will be assigned to the randomised treatment. Adverse events that start before first drug intake and deteriorate under treatment will also be considered as ‘treatment-emergent’.

All adverse events occurring before first drug intake and do not deteriorate under treatment will be assigned to ‘screening’ or ‘post-randomisation’ and all adverse events occurring after last drug intake will be assigned to ‘residual effect period’, ‘post-study’ or ‘follow-up’ (for listings only). Also, all AEs occurring between the start of an interruption and the end of interruption will be assigned to ‘off-treatment’ period in the listings. For details on the treatment definition, see [Section 6.1](#).

According to ICH E3 (7), AEs classified as ‘other significant’ will include those non-serious and non-significant adverse events which

- represents a marked hematological or other laboratory abnormality;
- led to an intervention, including withdrawal of drug treatment, dose reduction (‘action taken = discontinuation’ or ‘action taken = reduced’ for any of the study treatments), or significant additional concomitant therapy.

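### Protocol 5.3.7 counts all adverse events to last dose + 28 days as on-treatment, yet for early stoppers its exception asks only for related SAEs and AESIs from the day drug is stopped

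*Protocol*

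**What the plan says.** **Collection.** The general rule in Protocol 5.3.7 includes every AESI and sets this period and scope: "From signing the informed consent onwards through the Residual Effect Period (REP), until individual patient's end of trial: all AEs (serious and non-serious"). The next sentence, introduced as a contrast, concerns patients who stop trial medication prematurely but remain in the trial, including those for whom only a telephone or vital status contact is planned. For them, "from then on and until the individual patient's end of the trial the Investigator must report related SAEs and related AESIs".

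**Analysis window.** The same section sets the REP at 28 days after the last dose and says "All AEs which occurred through the treatment phase and throughout the REP will be considered as on treatment". Three other places agree:

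- Protocol 7.3.4 assigns to the treatment period "All adverse events with an onset between start of treatment and end of the residual effect period (REP"), again 28 days.
- SAP 6.1: "For safety analyses, data up to 28 days after last trial drug intake (included) will be considered on-treatment".
- SAP 7.8.1 uses the same window when it allocates events to the randomised arm: "all adverse events occurring between first drug intake until 28 days after last drug intake (end of the residual effect period) will be assigned".

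**Endpoint.** Protocol 5.1.2 lists as a secondary endpoint "Percentage of patients with on-treatment Serious Adverse Events (SAE) from baseline to week 24". Section 7.3.2 states that "Percentages of patients with on-treatment SAEs from baseline to week 24 will be compared using the Cochran-Mantel-Haenszel test", with risk ratios and risk differences. Neither section restricts the SAEs to related ones. Section 7.1 calls this analysis exploratory, and the endpoint is outside the testing hierarchy in 7.2.

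**The concern.** For a patient who stops early, the analysis counts 28 days in which the collection rule, read plainly, asks only for related SAEs and related AESIs. Unrelated non-fatal SAEs starting in that window and before week 24 would be absent from an endpoint meant to include them. Unrelated AESIs and all other non-serious events in the window would be absent from the treatment-emergent tables.

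Whether an SAE is counted then depends on a post-randomisation event (stopping) and on a causality opinion. That understates the SAE percentage, and it biases the arm comparison if stopping differs by arm. Sites may also follow different sentences of the same section. Safety of the combination is part of the primary objective (Protocol 2.2), and the SAP cannot restore events that were never entered.

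**Working it through.** **1. Where the exception starts.** The only event named before the words that start the restriction is the discontinuation of medication. The exception does not mention the REP. The on-treatment definition later in the section makes no allowance for early stoppers. The 28-day figure is the same in all four places that define the window, so the mismatch is in collection, not in the length of the window.

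**2. Whom it reaches.** Section 6.2.3 plans a week-24 vital status contact for early stoppers who decline visits. The bracket in 5.3.7 counts such a contact as staying in the trial. The exception therefore covers nearly all early stoppers except those who withdraw consent to the trial.

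**3. Possible size.** The documents give no figure to reproduce, so this is an illustration.

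*From the documents:* SAE proportions of 15% and 16% in the earlier sildenafil trial in IPF (Protocol 1.2.2), taken as 12-week (84-day) risks; 125 patients per arm; 24 weeks = 168 days.

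*Assumed:* a share p = 10–30% stops early, at times spread evenly over 168 days; the SAE hazard after stopping is m = 1–3 times the base rate; a share u = 80–95% of SAEs is judged unrelated.

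Daily hazard: λ = −ln(1 − r)/84.

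| r | λ per day | 28-day risk, 1 − exp(−28λ) | 24-week risk, 1 − (1 − r)² |
|---|---|---|---|
| 0.15 | 0.00193 | 5.3% | 27.8% |
| 0.16 | 0.00208 | 5.6% | 29.4% |

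A patient is lost to the endpoint only if no SAE occurred on drug before the stop at day s and an unreported one follows within the REP, capped at week 24:

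Missed = p × (1/168) × ∫₀¹⁶⁸ exp(−λs) × [1 − exp(−λ·m·u·min(28, 168 − s))] ds

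| Case | Stops over 24 weeks | Stops in first 12 weeks only |
|---|---|---|
| Minimum: r 0.15, p 0.10, m 1, u 0.80 | 0.34 points | 0.39 points |
| Maximum: r 0.16, p 0.30, m 3, u 0.95 | 3.60 points | 4.20 points |
| 10-point imbalance in stopping (p = 0.10, other inputs over their ranges) | 0.34–1.20 points | 0.39–1.40 points |

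The last column replaces 168 by 84 in the averaging and the upper limit of integration; the week-24 cap stays.

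Standard error of the risk difference at 28.5% risk: √(2 × 0.285 × 0.715/125) = 0.057, or 5.7 points. A shift of 1.2 points is 1.2/5.7 ≈ 0.2 standard errors.

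Fatal SAEs are not removed from these figures, although deaths are still captured through vital status and adjudication. The figures are therefore upper bounds for each set of assumptions.

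**4. A second conflict.** Section 6.2.3 ends the trial at visit 7 for early stoppers who keep attending. Flow-chart footnote 18 exempts them from the 28-day follow-up visit only if more than 28 days remain after the last dose. A patient who stops at week 22 has 14 days left at that point. That patient is finished under 6.2.3 but still owed a follow-up visit under footnote 18. This affects the treatment-emergent tables, not the week-24 SAE endpoint.

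**The case against.** The best counter-argument is that full capture was intended and would probably happen.

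- The general rule mentions the REP, so the exception could be meant to start after it. Figure 5.3.7:1 is not available here and may show that.
- The flow chart has an adverse-event row at every visit, including early end of treatment and follow-up. Footnote 17 and section 6.2.3 list what is dropped after an early stop, and adverse-event collection is not on either list.
- The paragraph in 5.3.7 on reporting to the sponsor has no relatedness filter. Patient files must hold all events, so some could be recovered from source.
- Acute exacerbations, a plausible source of serious unrelated events, have their own flow-chart row and all go to adjudication.
- Nothing in the documents supports a 10-point difference in stopping. Protocol 1.2.2 reports 3% discontinuation on both sildenafil 20 mg three times daily and placebo, although in pulmonary arterial hypertension.
- The sentence giving 15% and 16% states no period of its own.

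Most of this stands as evidence of intent and as reason to expect a small effect. Exacerbations captured by the separate route would lower the figures further, and the 12-week time base is an inference. But none of these passages says that the restriction waits until the REP ends, and an explicit exception is what a site would follow for eCRF entry. If the figure shows the later start, the sentence still has to be brought into line with it.

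**Conclusion.** The concern holds: as written, 5.3.7 requires less than the analysis counts for patients who stop early and stay in the trial. The loss is probably small, at 0.3–3.6 percentage points of patients per arm at most (0.4–4.2 if all stops fall in the first 12 weeks). The upper ends need every assumption at its extreme. Bias in the arm comparison requires unequal stopping, for which the documents give no evidence; a 10-point imbalance would move the risk difference by at most about 0.2 standard errors with stops spread over 24 weeks. Stopping share, hazard multiplier and unrelated share are assumptions.

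The primary endpoint and the confirmatory tests are not affected. The text should still be corrected, because uncollected events are hard to recover and the correction is cheap. Confidence is medium, mainly because the figure could not be seen.

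**What to change.** In Protocol 5.3.7, state that all AEs, SAEs and AESIs, whatever their relationship to trial medication, are collected for every patient who remains in the trial through the end of the REP (last dose + 28 days). State that the related-only limit starts after the REP. This is the version that matches the on-treatment definitions in 5.3.7, 7.3.4 and the SAP. Check that Figure 5.3.7:1 shows the same start.

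Separately, reconcile the end-of-trial bullet in 6.2.3 for early stoppers who keep attending with flow-chart footnote 18.

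The cost is protocol wording, a note to sites and a few more AE and SAE reports. No new procedure is needed.

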 13. Patients who complete an early End of Treatment visit and don't accept to attend all remaining planned visits will be contacted for vital status collection at week 24. This can be done by phone.
 14. Visit 2 is defined as baseline assessment if the respective parameter is planned to be collected at that visit. Otherwise, visit 1 will serve as baseline assessment.
 15. Visit 7 is the End of Treatment (EOT) visit for patients who complete the treatment period as planned.
 16. In case of dose change of nintedanib (reduction or re-escalation), dose adjustment visit must be conducted to allow dispensing of new medication kit.
 17. Early end of treatment visit to be completed for all patients who withdraw or discontinue all study drugs prematurely. These patients will be invited to attend all remaining visits as planned until week 24 (Visit 7). The following procedures are no longer required in the visits to be conducted after the early EOT visit: laboratory tests, biomarker sampling, pharmacokinetic sampling and ECG.
 18. A follow up visit needs to be completed 28 days (+7 days) after the last drug administration for all patients. Patients who prematurely discontinue all study drugs but accept to conduct all remaining study visits as planned and the remaining duration in the trial is longer than 28 days after the last drug administration are exempted from this visit.

TABLE OF CONTENTS

TITLE PAGE	1
CLINICAL TRIAL PROTOCOL SYNOPSIS	2
FLOW CHART	5
TABLE OF CONTENTS	7
ABBREVIATIONS	11
1. INTRODUCTION.....	13
1.1 MEDICAL BACKGROUND	13
1.2 DRUG PROFILE	14
1.2.1 Nintedanib.....	14
1.2.2 Sildenafil	16
2. RATIONALE, OBJECTIVES, AND BENEFIT - RISK ASSESSMENT	18
2.1 RATIONALE FOR PERFORMING THE TRIAL	18
2.2 TRIAL OBJECTIVES.....	19
2.3 BENEFIT - RISK ASSESSMENT.....	19
3. DESCRIPTION OF DESIGN AND TRIAL POPULATION.....	21
3.1 OVERALL TRIAL DESIGN AND PLAN	21
3.1.1 Administrative structure of the trial	21
3.2 DISCUSSION OF TRIAL DESIGN, INCLUDING THE CHOICE OF CONTROL GROUP(S)	23
3.3 SELECTION OF TRIAL POPULATION	23
3.3.1 Main diagnosis for trial entry	23
3.3.2 Inclusion criteria	24
3.3.3 Exclusion criteria	24
3.3.4 Removal of patients from therapy or assessments.....	27
3.3.4.1 Removal of individual patients	27
3.3.4.2 Discontinuation of the trial by the sponsor	28
4. TREATMENTS.....	29
4.1 TREATMENTS TO BE ADMINISTERED.....	29
4.1.1 Identity of BI investigational product and comparator product.....	29
4.1.2 Method of assigning patients to treatment groups.....	29

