3.1.1 Administrative structure of the trial

The sponsor of this trial is Boehringer Ingelheim (BI).

BI has appointed a Trial Clinical Monitor, responsible for coordinating all required activities, in order to

- manage the trial in accordance with applicable regulations and internal SOPs,
- direct the clinical trial team in the preparation, conduct, and reporting of the trial,
- ensure appropriate training and information of local clinical monitors (CML), Clinical Research Associates (CRAs), and Investigators of participating countries.

Data Management, Pharmacokinetic and Statistical Evaluation will be done by BI according to BI SOPs.

Tasks and functions assigned in order to organise, manage, and evaluate the trial will be defined according to BI SOPs. A list of responsible persons and relevant local information can be found in the ISF.

Additional information for Japan only: A list of responsible persons and relevant local information (as protocol reference, if applicable) can be found in the ISF.

A Coordinating Investigator will be nominated and will be responsible to coordinate Investigators at different centres participating in this multicentre trial. Tasks and responsibilities will be defined in a contract. Relevant documentation on the participating (Principal) Investigators and other important participants, including their curricula vitae, will be filed in the ISF.

Sites selected for participation will consist of specialized referral centres experienced in the management of IPF.

A DMC, independent of the sponsor, will be established to assess the progress of the clinical trial, including an unblinded safety assessment at specified intervals, and to recommend to the sponsor whether to continue, modify, or stop the trial. Measures are in place to ensure blinding of the sponsor and all other trial participants.

All death cases will be assessed (to evaluate the primary cause of death), as well as all adverse events categorized as major adverse cardiovascular events (MACE) and all acute IPF exacerbations (based on written clinical reports, for diagnostic confirmation) by an independent Adjudication Committee (AC), in a blinded manner before data base lock. The tasks and responsibilities of the DMC and the AC will be specified in a charter.

The DMC and the AC will maintain written records of all its meetings.

A central laboratory will perform all protocol specified blood analysis of the trial.

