5.2.3 Acute IPF exacerbations

Acute IPF exacerbations will be collected as adverse events.

Acute IPF exacerbation is defined as an acute, clinically significant, respiratory deterioration characterized by evidence of new widespread alveolar abnormality [[P16-06899](#)].

Extra-parenchymal causes (e.g. pneumothorax, pleural effusion, pulmonary embolism) should be excluded and the following 3 diagnostic criteria need to be met:

- Acute worsening or development of dyspnea typically of less than one month duration;
- Computed tomography with new bilateral ground-glass opacity and/or consolidation superimposed on a background pattern consistent with usual interstitial pneumonia pattern;
- Deterioration not fully explained by cardiac failure or fluid overload.

Events that are clinically considered to meet the definition of acute exacerbation of IPF but fail to meet the three diagnostic criteria due to missing computed tomography data will be termed “suspected acute exacerbations” by the Adjudication Committee.

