An “other significant adverse event” is defined as any non-serious adverse event which

- represents a marked haematological or other laboratory abnormality;
- led to an intervention, including withdrawal of drug treatment, dose reduction or significant additional concomitant therapy.

AEs considered “Always Serious”

Cancers of new histology and exacerbations of existing cancer must be reported as a serious event regardless of the duration between discontinuation of the drug and the occurrence of the cancer.

In accordance with the European Medicines Agency initiative on Important Medical Events, Boehringer Ingelheim has set up a list of further AEs, which by their nature, can always be considered to be “serious” even though they may not have met the criteria of an SAE as given above.

The latest list of “Always Serious AEs” can be found in the RDC system. These events should always be reported as SAEs as described in [section 5.3.7](#).

Adverse events of special interest (AESIs)

The term AESI relates to any specific AE that has been identified at the project level as being of particular concern for prospective safety monitoring and safety assessment within this trial, e.g. the potential for AEs based on knowledge from other compounds in the same class. AESI

need to be reported to the sponsor's Pharmacovigilance Department within the same timeframe that applies to SAEs, see [section 5.3.7](#).

The following are considered AESIs:

Adverse events relating to gastrointestinal perforation

and

Hepatic injury

In this study protocol, signs of hepatic injury are defined as:

- ALT and/or AST \geq 8 fold ULN
- ALT and /or AST \geq 3 fold ULN and total bilirubin \geq 2 fold ULN*
- ALT and /or AST \geq 3 fold ULN and unexplained INR > 1,5*
- ALT and /or AST \geq 3 fold ULN and unexplained eosinophilia (>5%)*
- ALT and /or AST \geq 3 fold ULN and appearance of fatigue, nausea, vomiting, right upper abdominal quadrant pain or tenderness, fever and/or rash

* in the same blood draw sample.

These lab findings constitute a hepatic injury alert and the patients showing these lab abnormalities need to be followed up according to the "DILI checklist" provided in the ISF.

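### Protocol 5.3.7 narrows event reporting after early discontinuation to related SAEs and AESIs, which conflicts with the flow chart, 6.2.3 and 3.1.1 on acute IPF exacerbations and may lead to under-reporting in off-drug patients who still attend visits

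*Protocol*

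**What the plan says.** Five places in the protocol bear on this.

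- **Section 5.2.3**, under the efficacy assessments: "Acute IPF exacerbations will be collected as adverse events".
- **Section 5.3.7** opens with a broad rule. From consent onwards the eCRF must capture events "through the Residual Effect Period (REP), until individual patient's end of trial: all AEs (serious and non-serious) and all AESIs". It then makes an exception: "if an individual patient discontinues trial medication prematurely but stays in the trial", then from that time until the patient's end of trial "the Investigator must report related SAEs and related AESIs". The same section sets the REP at 28 days after the last dose and states: "All AEs which occurred through the treatment phase and throughout the REP will be considered as on treatment".
- **Section 5.3.6.1** names two kinds of AESI. The first is "Adverse events relating to gastrointestinal perforation" and the second is hepatic injury. Acute exacerbation is not listed.
- **Flow chart and section 6.2.3.** Acute exacerbations have a row of their own, separate from adverse events and marked at every visit. For patients who keep attending after early end of treatment, footnote 17 lists what is "no longer required in the visits to be conducted after the early EOT visit: laboratory tests, biomarker sampling, pharmacokinetic sampling and ECG". Section 6.2.3 lists the same omissions, with laboratory tests optional. Neither drops the exacerbation review.
- **Section 3.1.1** gives the scope of blinded adjudication as "all acute IPF exacerbations (based on written clinical reports, for diagnostic confirmation) by an independent Adjudication Committee (AC", with no condition on causality, seriousness or treatment status.

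**The concern.** Section 5.2.3 makes the adverse event record the stated route for an outcome that the protocol places under efficacy and sends to an independent committee. Section 5.3.7 then narrows that route once a patient stops drug early. To be reportable, an exacerbation would have to be both serious and judged related. The causality guidance in 5.3.6.1 counts underlying disease as an argument against relatedness, so an IPF exacerbation in a patient off drug will often be called unrelated.

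The committee works from written clinical reports and can adjudicate only what is sent to it. If one site follows 5.3.7 and another follows the flow chart, off-drug capture depends on the site. In any time-to-event analysis that runs to week 24, an unreported event in a patient who is still attending would look like event-free follow-up. It would not appear as missing data.

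There is a side effect on safety. If the restriction starts at the last dose, unrelated SAEs during the REP need not be reported, yet they count as on treatment and so belong in the secondary endpoint of patients with on-treatment SAEs.

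**Working it through.** **1. The rules set side by side**, for a patient who has stopped all drugs early and still attends visits:

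| Place | Unrelated or non-serious exacerbation |
|---|---|
| 5.3.7, exception | Not required |
| 5.3.7, general rule and REP sentence | Required, at least to 28 days after last dose |
| Flow chart row, footnote 17, 6.2.3 | Assessed at each remaining visit |
| 3.1.1 | Adjudicated |

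**2. Two hypothetical cases.**
- Last dose at week 8, exacerbation at week 18 judged serious but unrelated. This is 10 weeks (70 days) after the last dose, so outside the REP. The exception in 5.3.7 does not require a report. The flow chart and 3.1.1 require capture and adjudication.
- Last dose at week 8, the same event at week 10. This is 14 days after the last dose, so inside the REP. The answer depends on whether the exception starts at the last dose or when the REP ends. The visible text supports either.

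**3. Size.** The plan gives no figure of its own for exacerbations in this trial, so this is an illustration only.

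Inputs from the protocol: 250 patients, 24 weeks, a 28-day (4-week) REP, and 5–10% of IPF patients with an exacerbation each year (section 1.1, general IPF population).

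Assumptions: 10–30% stop all drugs early (the documents give no rate), stopping times are uniform over 24 weeks, everyone who stops keeps attending, and risk is equal on and off drug.

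- Hazard per year: h = −ln(1 − 0.05) = 0.0513, and −ln(1 − 0.10) = 0.1054.
- Patients with an event in 24 weeks: 250 × (1 − exp(−h × 24/52)) = 5.8 and 11.9, or about 6–12.
- Mean off-drug time per patient who stops: 24/2 = 12 weeks. Beyond the REP: (20²/2)/24 = 8.33 weeks.
- Off-drug person-weeks: 250 × 0.10 × 12 = 300, up to 250 × 0.30 × 12 = 900. This is 5–15% of the 6,000 person-weeks.
- Events exposed to the exception from the last dose: 300/52 × 0.0513 = 0.3, up to 900/52 × 0.1054 = 1.8.
- Beyond the REP only: 250 × 0.10 × 8.33 = 208 person-weeks gives 208/52 × 0.0513 = 0.2. At the top, 250 × 0.30 × 8.33 = 625 gives 625/52 × 0.1054 = 1.3.
- With the on-drug rate held fixed, exposed events scale with the off-drug rate. Doubling it gives about 0.6–3.6 from the last dose, or 0.4–2.5 beyond the REP.

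Exposed does not mean lost. Related serious events are still reported, and sites following the flow chart would record the rest.

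**The case against.** The strongest reply is that the protocol already requires capture. Exacerbations have their own flow-chart row, off-drug visits keep every procedure except a short list, and 5.3.7 asks investigators to keep detailed records of all adverse events in the patient files. It also asks for worsening of the underlying disease to be recorded. The restricting sentence does not contain the word *only*, whereas the next one, on events after end of trial, does, so it can be read as a minimum duty. All deaths are adjudicated for cause, so a fatal exacerbation in a followed patient should reach the committee. The REP wording can be read as full collection for 28 days after the last dose. The adverse event collection figure in 5.3.7 was not available for this review and may settle the start point.

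Most of this stands, and it limits the point. A reader might infer that off-drug exacerbations go uncollected, or that the adverse event page is the only route. The separate row and 6.2.3 do not support either. A reader might also infer that the loss falls on the highest-risk patients and differs by arm. The documents give no risk data for patients who stop, list many reasons for stopping that are unrelated to decline (section 3.3.4.1), and describe a double-blind trial.

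Nor can it be said that a planned efficacy analysis is compromised. Exacerbation is neither a primary nor a secondary endpoint, and the further-endpoint sections are not in the supplied text. The synopsis mentions Kaplan-Meier and Cox methods without naming an endpoint, and the retention of off-drug data in SAP 7.4.1 concerns SGRQ only.

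What the reply does not do is remove the contradiction. The sentence in 5.3.7 begins as an exception to collecting everything, so a site has good reason to read it as a limit.

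**Conclusion.** The conflict is real, and nothing in the supplied text resolves it. Unrelated or non-serious exacerbations in off-drug patients who still attend visits may be under-reported, at least after the REP, and capture may differ between sites. At equal risk the exposure is about 0.3–1.8 events out of some 6–12, or 0.2–1.3 if the REP is fully collected. It is larger if risk is higher off drug or if this advanced population exceeds the general IPF rate. These figures rest on an assumed 10–30% stopping rate and on all who stop continuing to attend.

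The primary and secondary SGRQ and UCSD SOBQ analyses, their testing hierarchy and the sample size are untouched. Whether exacerbation is a formal further endpoint cannot be confirmed here. With so few events expected, one or two missed would still matter to a comparison between arms, and the correction is cheap.

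**What to change.** Make two changes in section 5.3.7.

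1. State whether *from then on* starts at the last dose or after the 28-day REP, and make it consistent with the on-treatment definition in that section and in SAP 6.1.
2. Add a sentence such as: *Acute IPF exacerbations are recorded and sent for adjudication regardless of seriousness or causality until week 24 for every randomised patient who remains in follow-up, including after discontinuation of all trial drugs.*

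Mirror this in the eCRF completion guidance. The visits, the flow-chart row and the committee already exist, so the cost is the wording and a few more events to document and adjudicate. The change concerns data collection only. It does not recover exacerbations in patients who decline further visits and give vital status only.
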